8.0 STUDY POPULATION

8.1 Inclusion Criteria

Patients who meet *all* of the following criteria are eligible to participate in the study:

8.1.1 Demographic Characteristics:

1. Male and female patients, age ≥ 18 years at time of signing informed written consent

8.1.2 SSc and SSc-ILD Related Criteria:

2. Confirmed diagnosis of diffuse cutaneous systemic sclerosis/scleroderma fulfilling the 2013 American College of Rheumatology (ACR)/European League Against Rheumatism (EULAR) criteria for systemic sclerosis/scleroderma [151].
3. Disease duration ≤ 60 months defined as the time from the first non-Raynaud's phenomenon manifestation.
4. mRSS ≥ 15 and ≤ 45
5. Diagnosis of SSc-ILD based on a HRCT chest scan completed within 3 months prior to the date of written informed consent at medication washout or screening, as applicable. The HRCT chest scan must demonstrate features consistent with SSc-ILD, as confirmed following review of the HRCT images by Mayo radiology study staff. If the HRCT chest study is determined to be technically inadequate (for example, prone imaging not included), or cannot be made available for review by Mayo radiology study staff, or if the HRCT chest was performed more than 3 months prior to signing of written informed consent, a HRCT chest scan will be obtained during study screening.

6. Screening pulmonary function testing demonstrating FVC \geq 45% predicted and DLCO \geq 40% predicted. Pulmonary function testing previously completed as part of clinical care within the prior 3-12 months will be used to compare screening results with prior testing to determine there has not been an interim decline of FVC \geq 15 % predicted or decline of DLCO \geq 15% predicted. Only if both FVC % predicted and DLCO % predicted are observed clinically stable will the patient be considered eligible for participation.
7. Screening resting transthoracic echocardiogram within 6 months of providing written informed consent at medication washout or screening, as applicable, demonstrating estimated right ventricular systolic pressure of \leq 40 mm Hg, no evidence of right atrial or right ventricular enlargement, and left ventricular ejection fraction \geq 40%.
8. At study entry, the participant is either not taking any background SSc-ILD medication or is taking background MMF, as described below:
 - a. Not on background SSc-ILD medication**

Participant has not taken background medication specifically for SSc-ILD in the 3 months before study screening or will complete appropriate washout of SSc-ILD medications other than MMF by time of study screening. For such patients, there must be no plan to start SSc-ILD medication during the study.
 - b. Taking background MMF**

Participant is taking background MMF (\leq 1.5 g twice daily), and the dose has been stable during the 3 months before study Day 1.

8.1.3 Informed Consent and Protocol Adherence:

9. Able to understand and sign a written informed consent form
10. Able to understand the importance of adhering to study treatment and the study protocol, and willing and able to follow all study requirements, including the concomitant medication restrictions, throughout the study
11. Use of effective contraception:

Women of childbearing potential are required to have a negative pregnancy test before treatment and must agree to maintain highly effective contraception by practicing abstinence or by using at least two methods of birth control from the date of providing written informed consent through the end of the study (see 14.0 Pregnancy). The six participants enrolled in the study group already using mycophenolate background medication will have been previously counseled as found clinically indicated on the use of IUD mechanical contraception, as mycophenolate interferes with effectiveness of hormonal contraceptives. The six participants enrolled in the study group not using background mycophenolate, if not abstinent, will be required to be using an oral contraceptive or an IUD as one

of the two methods for birth control. The additional use of a spermicide or other standard means of contraception is acceptable in both study groups.

12. Male patients, even if surgically sterilized (i.e., status post-vasectomy), must agree to one of the following (see 14.0 Pregnancy):
 - Agree to practice effective barrier contraception during the entire study treatment period and through 90 days after the last dose of study drug, OR
 - Agree to practice true abstinence when this is in line with the preferred and usual lifestyle of the subject. Periodic abstinence (e.g., calendar, ovulation, symptothermal, post-ovulation methods] and withdrawal are not acceptable methods of contraception.

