10. History of a clinically significant environmental exposure that is known to cause pulmonary fibrosis including, but not limited to, drugs (e.g., amiodarone), asbestos, beryllium, radiation, or domestic birds or other exposures associated with hypersensitivity pneumonitis
11. Tobacco smoking within 3 months of screening or unwillingness to avoid smoking throughout the study (e.g., cigarette, pipe, or cigar)
12. History of unstable or deteriorating cardiac disease within the previous 6 months relative to study Day 1 including, but not limited to, the following:
 - a. Unstable angina pectoris
 - b. Myocardial infarction
 - c. Congestive heart failure requiring hospitalization
 - d. Uncontrolled clinically significant arrhythmia
 - e. Clinically significant pericardial effusion
 - f. Pulmonary hypertension (see 8.2.1 Exclusion Criteria - Disease Related)
13. Known underlying liver disease (e.g., hepatitis or cirrhosis)
14. Known or suspected peptic ulcer
15. Known active hematologic disorder other than anemia of chronic disease or iron deficiency anemia (hemoglobin < 8.0 gm/dl).
16. Known hematologic malignancy
17. History of any malignancy within the last 5 years other than non-melanoma skin cell cancers cured by local resection or carcinoma-in-situ
18. Prior stem cell or bone marrow transplant
19. Any condition that might be significantly exacerbated by the known side effects associated with ixazomib including known \geq grade 2 peripheral neuropathy
20. Pregnancy or lactation: Positive pregnancy test; currently lactating; or for women of childbearing potential and men, an unwillingness to maintain abstinence or highly effective contraception (see 8.1.3 Eligibility Criteria – Informed Consent and Protocol Adherence)

21. History of alcohol or substance abuse in the previous 2 years relative to study Day 1.
22. Expected to have study participation interrupted for a foreseeable medical or surgical event (e.g., organ, stem cell, or bone marrow transplant; orthopedic-related surgery).
23. Any condition that is likely to result in the death of the patient within 12 months.
24. History of known or active COVID19 infection.

8.2.3 Laboratory Exclusions:

25. Any of the following screening test criteria:
 - a. Hemoglobin \leq 8.0 gm/dl
 - b. Absolute neutrophil count \leq 1000
 - c. Platelet count \leq 75,000

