14.0 PREGNANCY

It is not known what effects ixazomib has on human pregnancy or development of the embryo or fetus. Therefore, female patients participating in this study should avoid becoming pregnant, and male patients should avoid impregnating a female partner. Nonsterilized female patients of reproductive age group and male patients should use effective methods of contraception through defined periods during and after study treatment as specified below.

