14.1 Female patients

Female patients must meet 1 of the following:

- Postmenopausal for at least 1 year before the screening visit, or
- Surgically sterile, or
- If they are of childbearing potential, agree to practice 2 effective methods of contraception from the time of signing of the informed consent form through 90 days after the last dose of study drug (See 8.1.3 Study Population Informed Consent and Protocol Adherence), or
- Agree to practice true abstinence, when this is in line with the preferred and usual lifestyle of the subject. (Periodic abstinence [e.g., calendar, ovulation, symptothermal, postovulation methods] and withdrawal are not acceptable methods of contraception.)

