17.2.3 Clinical Laboratory Tests

All clinical laboratory tests will be performed by Mayo Clinic Laboratory:

- **Hematology:** complete blood cell count with automated differential and platelet count, erythrocyte sedimentation rate (ESR) and C-Reactive Protein (CRP).
- **Serum Chemistry:** albumin, alkaline phosphatase, ALT, AST, bicarbonate, direct bilirubin, indirect bilirubin, total bilirubin, calcium, cholesterol, chloride, creatine kinase (CK), creatinine, triglycerides, glucose, lactate dehydrogenase (LDH), magnesium, phosphorus, potassium, total protein, sodium, urea nitrogen, and uric acid.
- **Clinical Immunology:** serum protein immunoelectrophoresis, quantitative immunoglobulins (IgG, IgA, IgM), and IgG tetanus toxoid titer.

The hematology, serum chemistry, and clinical immunology lab tests will be obtained at screening, study day 1, day 28 (week 4), day 56 (week 8), day 84 (week 12), day 112 (week 16), day 140 (week 20), day 168 (week 24), and at the concluding follow-up study day 196-203 (week 28-29) office visits for participants not proceeding on to the extension study.

Additional lab visits are scheduled day 14 (week 2), day 42 (week 6), and day 70 (week 10) for monitoring hematology and serum chemistry tests between study office visits during the first three ixazomib cycles. For the extension study, hematology and serum chemistry tests will be obtained at study day 28 (week 28), day 56 (week 32), day 84 (week 36), day 112 (week 40), day 140 (week 44), day 168 (week 48), and at the concluding follow-up study day 196-203 (week 52-53) office visits.

Specified clinical laboratory assessments will be obtained more frequently if clinically indicated and in conjunction with other laboratory assessments as required.

- **Pregnancy Test** (women of childbearing potential): serum pregnancy test will be performed at screening, on study Day 1; day 28 (week 4), day 56 (week 8), day 84 (week 12), day 112 (week 16), day 140 (week 20), day 168 (week 24), and day 196-203 (week 28-29) follow-up visit for participants not proceeding on to the extension study. For the extension study, serum pregnancy test will be obtained at study day 28 (week 28), day 56 (week 32), day 84 (week 36), day 112 (week 40), day 140 (week 44), day 168 (week 48), and at the concluding follow-up study day 196-203 (week 52-53) office visits.

17.2.4 12-Lead Electrocardiogram

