23.3 Procedures for Reporting Drug Exposure During Pregnancy and Birth Events

If a woman becomes pregnant or suspects that she is pregnant while participating in this study or within 90 days after the last dose, she must inform the investigator immediately and permanently discontinue study drug. The sponsor-investigator must immediately fax a completed Pregnancy Form to the Takeda Department of Pharmacovigilance or designee. The pregnancy must be followed for the final pregnancy outcome.

If a female partner of a male patient becomes pregnant during the male patient's participation in this study, the sponsor-investigator must also immediately fax a completed Pregnancy Form to the Takeda Department of Pharmacovigilance or designee. Every effort should be made to follow the pregnancy for the final pregnancy outcome.

Suggested Pregnancy Reporting Form: Pregnancy Report Form (provided by Takeda)

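### Inclusion criterion 11 gives an earlier end date for female contraception than section 14.1, and women who enter post-discontinuation monitoring lose the follow-up pregnancy test

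*Combined protocol and SAP*

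**What the plan says.** **End of contraception.** Criterion 11 in 8.1.3 requires women of childbearing potential to use contraception "from the date of providing written informed consent through the end of the study (see 14.0 Pregnancy"). Section 14.0 opens by asking for "effective methods of contraception through defined periods during and after study treatment as specified below", and 14.1 sets the female period "from the time of signing of the informed consent form through 90 days after the last dose of study drug", with a reference back to 8.1.3. Criterion 12 asks men for "effective barrier contraception during the entire study treatment period and through 90 days after the last dose of study drug", and 14.2 repeats this. Section 23.3 requires a woman to report a pregnancy that occurs "while participating in this study or within 90 days after the last dose". Exclusion 20 bars "an unwillingness to maintain abstinence or highly effective contraception (see 8.1.3 Eligibility Criteria" and so points to 8.1.3, not to 14.1. Section 9.3 gives the total study duration as 28-29 weeks from Day 1, unchanged if dosing is interrupted.

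**Pregnancy tests.** Section 17.2.3 schedules a serum test at every monthly visit through day 168, "and day 196-203 (week 28-29) follow-up visit for participants not proceeding on to the extension study". A woman who stops early has the day 168 assessments, which include a test (15.0 with 18.3.10 item 10; 25.3.1 with 25.2.7 item 10). The follow-up visit 28-35 days later holds the next one (18.3.11 item 6; 25.2.8 item 6). Sections 15.1.2 and 25.4.2 remove that follow-up visit for anyone who starts post-discontinuation monitoring. The monitoring lists in 15.1.3 to 15.1.5 and 25.4.2.1 to 25.4.2.3 contain no pregnancy test, and 17.2.3 names no monitoring visit.

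**The concern.** One safety rule has two end dates. The earlier one stands in the eligibility text, which is where exclusion 20 directs staff. Criterion 11 and 14.1 refer to each other, and neither says which prevails. A woman counselled from 8.1.3 alone could be given a date weeks short of the one in 14.1, for a drug whose effects on human pregnancy the protocol calls unknown (14.0).

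The second issue is an omission. The protocol encourages women who stop early to accept monitoring, yet those who accept have one scheduled pregnancy test fewer than those who decline, although blood is drawn at every monitoring visit. After the early discontinuation visit, detection rests on self-report (23.3) or on a test ordered because it is clinically indicated (17.2.3, 19.0).

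**Working it through.** The plan states no figure for either gap, so this is day counting from its schedule.

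**Inputs.** Cycle 6 day 1 is at the day 140 visit (18.3.9). Doses are on cycle days 1, 8 and 15. Study end is day 196-203 (9.3: 28 × 7 = 196, 29 × 7 = 203; 18.3.11). The early discontinuation visit is due within 10 days of the last dose (15.0), with follow-up 28-35 days after it. Office visits and post-discontinuation (PD) visits carry ±4 days.

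**Completer, criterion 11 read alone.**
- Last dose: 140 + 14 = day 154. 90-day point: 154 + 90 = day 244.
- Shortfall: 244 − 203 = 41 to 244 − 196 = 48 days.
- With visit windows: last dose day 150-158, follow-up day 192-207, so follow-up comes 192 − 158 = 34 to 207 − 150 = 57 days after the last dose. Shortfall: 90 − 57 = 33 to 90 − 34 = 56 days.
- The extension has the same layout and gives the same figures.

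**Early discontinuer, criterion 11 read alone.** The answer depends on what the end of the study means.
- Calendar reading (9.3): no shortfall if the last dose is on or before day 106, since 106 + 90 = 196.
- Own-last-visit reading (7.1 and 15.0 discontinue her from the study), monitoring declined: see the table. A stop at a scheduled visit, before that day's dose, comes 28 − 15 = 13 days (cycle 1) or, for example, 56 − 42 = 14 days after the previous day 15 dose, so it already misses the 10-day window. An adverse event (AE) interruption of more than 28 days puts the discontinuation visit at day 29 or later.

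| Route to stopping | Discontinuation visit, days after last dose | Follow-up visit if monitoring declined | Shortfall against 90 days |
|---|---|---|---|
| 10-day window met | 0-10 | 0 + 28 = 28 to 10 + 35 = 45 | 45-62 |
| Stop at a scheduled visit | about 13-14 | 13 + 28 = 41 to 14 + 35 = 49 | about 41-49 |
| AE interruption >28 days | 29 or later | 29 + 28 = 57 or later | at most 33 |

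**Last scheduled pregnancy test.** A woman who declines monitoring has it at the follow-up visit (third column). A monitored woman has it at the discontinuation visit (second column). A completer has it 196 − 154 = 42 to 203 − 154 = 49 days after the last dose.

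**Where criterion 11 is the longer rule.** A monitored woman's final visit falls on day 168-203 (15.1.5). If her last dose was cycle 3 day 15 (56 + 14 = day 70), the 90-day point is day 160, before that visit.

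**A test at PD Visit 1** (28 ± 4 days after the discontinuation visit) would fall at 0 + 24 = 24 to 10 + 32 = 42 days if the window is met. It would fall at 13 + 24 = 37 to 14 + 32 = 46 days for a stop at a scheduled visit, and at 29 + 24 = 53 days or later after the long interruption. Each is close to the follow-up timing in the table.

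**The case against.** The strongest reply on contraception is that the protocol already resolves it. Criterion 11 cites 14.0 in the same sentence, 14.1 is mandatory, nothing in criterion 11 waives it, and criterion 10 requires a participant to be "willing and able to follow all study requirements, including the concomitant medication restrictions, throughout the study". This stands: both rules apply and the longer governs. A reader might infer that the plan releases women from contraception 41-48 days too soon. It does not; that figure measures criterion 11 in isolation. Nor can one say that women will be told the wrong date, because the consent pages are not in the supplied text.

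On testing, a reader might infer that monitored women go untested after stopping. That is also too strong: they are tested at the early discontinuation visit, they are off drug, and self-report and clinically indicated tests remain. Appendix A, cited in 19.0, was not supplied. Its title covers washout through follow-up, so it may or may not address monitoring visits.

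A further fair point concerns the remedy. Simply copying 14.1 into criterion 11 would shorten coverage for some early stoppers in monitoring, as the day 70 example shows. The fix has to avoid that.

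**Conclusion.** Both parts hold, and both are minor.

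1. Criterion 11 and 14.1 give different end dates. For an on-schedule completer, criterion 11 alone is 41-48 days short. For early discontinuers the difference runs from none (calendar reading, last dose by day 106) to 62 days (own last visit, monitoring declined), depending on a term that the protocol does not tie down for them. Confidence in the inconsistency is high.
2. On the printed visit lists and 17.2.3, women in post-discontinuation monitoring have one scheduled pregnancy test fewer than women who decline it. The contrast is 0-10 against 28-45 days after the last dose when the visit window is met, and about 13-14 against 41-49 days for a stop at a scheduled visit. After a long AE interruption the monitored woman's last test is already at 29 days or later, so her need is smaller. Confidence is moderate while Appendix A is unseen.

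The testing gap reaches only those women of childbearing potential, among 12 participants, who stop early and choose monitoring. The documents give no expected number.

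**What to change.** 1. In criterion 11 and in 14.1, state that contraception runs to the end of the study or to 90 days after the last dose of study drug, whichever is later. This removes the conflict, agrees with the reporting window in 23.3 and shortens no woman's coverage.
2. Add a serum pregnancy test for women of childbearing potential at PD Visit 1 (15.1.3) and at Visit 1 of extension-study monitoring (25.4.2.1), or at the final monitoring visit (15.1.5, 25.4.2.3) if that comes first. Name it in 17.2.3, and check that Appendix A agrees.

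**Cost.** One phrase in each of 8.1.3 and 14.1, and one line in each of 15.1.3, 15.1.5, 25.4.2.1, 25.4.2.3 and 17.2.3. There is one extra assay per affected woman, on blood already drawn for hematology and chemistry. Some early stoppers would continue contraception to the end of monitoring, beyond the 90-day point, which criterion 11 already requires of them.

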 - d. Total bilirubin above $1.5 \times$ upper limit of the normal range (ULN), except in patients with predominantly unconjugated hyperbilirubinemia (e.g., Gilbert's syndrome)
 - e. Aspartate or alanine aminotransferase (AST or ALT) $>2 \times$ ULN
 - f. Alkaline phosphatase $>2 \times$ ULN
 - g. Creatinine clearance <30 mL/min

8.2.4 Medication Exclusions:

26. Any prior use of ixazomib or other proteasome inhibitor
27. Any prior use of rituximab
28. Any prior use of cyclophosphamide
29. Suspected intolerance, allergy, or hypersensitivity to ixazomib or any of its excipients
30. Ongoing use or expected use of any of the following therapies:
 - a. Investigational drug within the 28 days before screening (an investigational drug is defined as any drug that has not been FDA approved for marketing)
 - b. Strong CYP3A inducers (e.g. rifampin, rifapentine, rifabutin, carbamazepine, enzalutamide, phenytoin, fosphenytoin, phenobarbital, St. John's wort)
 - c. Methotrexate
 - d. Leflunomide
 - e. Azathioprine
 - f. Sirolimus
 - g. Tacrolimus
 - h. Oral corticosteroids at a dose >10 mg/d prednisone equivalent
 - i. D-penicillamine
 - j. Minocycline
 - k. Interferon- γ

- i. Endothelin-1 receptor antagonists (e.g., bosentan, ambrisentan or macitentan)
- m. Phosphodiesterase inhibitors (for use other than erectile dysfunction or Raynaud's phenomenon)
- n. Riociguat
- o. Tumor necrosis factor- α (TNF- α) inhibitor drugs
- p. Tocilizumab
- q. Rituximab
- r. Abatacept
- s. Cyclosporine
- t. Cyclophosphamide
- u. Intravenous immunoglobulin (IVIG)
- v. Nintedanib

8.2.5 General Exclusion:

- 31. Unsuitable for enrollment or unlikely to comply with study requirements, as assessed by the investigator

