10.0 BACKGROUND MEDICATION MMF

The study will enroll participants who either are not on background SSc-ILD medication or are on a background stable dose of MMF (see Study Population 8.1.2 SSc and SSc-ILD Related Criteria). MMF will be treated as background medication and will continue to be prescribed as part of usual clinical care. MMF will not be provided as part of the study. Participants on MMF will continue to take MMF during the study. Background MMF cannot be switched to another agent, nor is the addition of other background medications permitted; if this is necessary, the patient will be discontinued from the study and will proceed to complete early discontinuation assessments and procedures. Changes in the dose of the background MMF are not planned during the study; but if patient management requires a dose adjustment within the established limits of MMF ≤ 1.5 g BID, the patient will remain in the study. Changes within the allowable dose range of MMF will not be considered a deviation. MMF can produce significant adverse effects, including effects on the GI system, skin, liver, and central nervous system. Participants will be monitored for adverse effects of MMF when being used concurrently with ixazomib.

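### Criterion 11 requires a named contraceptive method only for women not on MMF, and expressly rules out oral contraceptives nowhere for women on MMF, although it says MMF weakens them

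*Combined protocol and SAP*

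**What the plan says.** Criterion 11 in section 8.1.3 sets one rule for women of childbearing potential in both groups: they "must agree to maintain highly effective contraception by practicing abstinence or by using at least two methods of birth control". The period runs "from the date of providing written informed consent through the end of the study", with a pointer to section 14.0.

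The criterion then treats the groups differently. Non-abstinent women not on MMF "will be required to be using an oral contraceptive or an IUD as one" of the two methods. The six participants on MMF "will have been previously counseled as found clinically indicated on the use of IUD mechanical contraception, as mycophenolate interferes with effectiveness of hormonal contraceptives". A closing sentence covers everyone: "The additional use of a spermicide or other standard means of contraception is acceptable in both study groups".

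Other sections bear on the point:

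- Exclusion 20 (8.2.2) rejects candidates who show "an unwillingness to maintain abstinence or highly effective contraception" and refers back to 8.1.3.
- Section 14.1 asks for two effective methods, makes no distinction by MMF use, and also refers back to 8.1.3. It runs to 90 days after the final dose and defines true abstinence.
- Section 10.0 says that "MMF will be treated as background medication and will continue to be prescribed as part of usual clinical care" and contains no contraception rule.
- Exclusion 31 (8.2.5) lets the investigator turn away anyone judged "Unsuitable for enrollment or unlikely to comply with study requirements, as assessed by the investigator".

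**The concern.** The protocol names a hazard and attaches a requirement only to the group that does not face it. Women not on MMF are told which method must be one of the two. Women on MMF, the drug said to weaken hormonal contraception, are told only what they will already have heard in routine care, where clinically indicated. Whether a given pair of methods is acceptable for them is left to judgment case by case.

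The stakes are fetal exposure. Section 9.1.2 calls ixazomib cytotoxic, section 14.0 says its effect on human pregnancy is unknown, and section 5.0 says it has not been studied together with MMF. Section 1.1 describes scleroderma patients as 80% women aged 30-50, so women of childbearing potential are likely to be among those enrolled.

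Separately, criterion 11 gives an earlier end date for contraception than 14.1 and mentions abstinence without 14.1's definition.

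**Working it through.** **Does any provision exclude an oral contraceptive plus spermicide for a woman on MMF?** This is a reading exercise and needs no arithmetic.

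| Provision | Effect on that pair |
|---|---|
| Criterion 11, general rule | Two methods are present, so it is met literally |
| Criterion 11, named-method clause | Applies only to the group without MMF |
| Criterion 11, counseling sentence | Describes past, conditional advice; sets no condition of entry |
| Criterion 11, closing sentence | Spermicide is acceptable as an additional method in both groups |
| Exclusion 20 | Uses an undefined standard and points back to 8.1.3 |
| 8.2.4 and 13.0 | Hormonal contraceptives are in neither list |
| 10.0 | Says nothing on contraception |
| 14.1 | Two effective methods, undefined, not split by MMF use |
| Exclusion 31 | The investigator may refuse, at discretion |

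No row excludes the pair expressly. Three rows (exclusion 20, 14.1 and exclusion 31), together with criterion 11's own effectiveness standard, give an investigator grounds to refuse it. An oral contraceptive alone fails at the first row, because two methods are needed.

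**How far apart are the two end dates?** This uses the nominal schedule.

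- Cycle 6 day 1 is taken at the day 140 visit (18.3.9), so cycle 6 day 15 falls on day 140 + 14 = 154.
- Section 14.1 ends on day 154 + 90 = 244.
- Criterion 11, read alone, ends with the follow-up visit on day 196-203 (18.3.11).
- Difference: 244 - 203 = 41 days to 244 - 196 = 48 days.

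The extension repeats the same visit numbering, so its nominal difference is the same. Held or late doses and early discontinuation shift these dates, so 41-48 days describes the nominal schedule and is not a bound.

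**How many people and doses?** Six of the 12 planned participants take MMF (7.1). Those concerned are the non-abstinent women of childbearing potential among them who would use a systemic hormonal method: at most 6, possibly 0. A full course is 3 x 6 = 18 ixazomib doses, or 3 x 12 = 36 with the extension.

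**The case against.** The best defence is that the text, read as a whole, already points to an IUD. Criterion 11 asks for highly effective contraception, 14.1 asks for two effective methods, and criterion 11 itself says MMF reduces the effectiveness of hormonal contraceptives. A method the protocol calls impaired is a poor candidate for one of two effective ones. The closing sentence speaks of additional use of a spermicide, which presupposes a main method in each group, and the only one named for the MMF group is the IUD. The practical room for misreading is also small: 12 patients from one programme in an investigator-initiated study. The consent pages are not in the extract, so participants may have received clearer instructions.

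Much of this stands. A reader might infer that nothing stops a woman on MMF from relying on the pill. That is too strong, because the pill could not be her only method and the effectiveness terms give grounds to refuse it as one of two. What remains is that those terms are undefined, the exclusion that uses one of them points back to the criterion, and the drafters wrote a requirement for one group and not for the other.

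Pregnancy testing is a second defence. Serum tests at screening, Day 1, each 28-day visit and follow-up (17.2.3), with immediate discontinuation if pregnant (22.0), shorten exposure but do not prevent it. The post-discontinuation visit lists in 15.1.3 to 15.1.5 include no pregnancy test, and participants in that monitoring skip the day 196-203 visit (15.1.2).

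On the end date, the defence largely succeeds. Criterion 11 refers to section 14.0, and 14.1 gives both the 90-day period and the definition of abstinence.

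**Conclusion.** The point holds as a low-severity safety clarification. Criterion 11 attaches a required method only to women not on MMF. For women on MMF the intended method appears to be an IUD, but this has to be inferred, and an oral contraceptive plus spermicide satisfies the literal rule.

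The size cannot be measured from the documents. They do not say how much MMF reduces hormonal effectiveness, or how many of the six MMF participants will be non-abstinent women of childbearing potential using such a method. The ceiling is 6 of 12 and the floor is zero. No endpoint or analysis is affected.

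A reader might also infer from the 41-48 day difference that women go unprotected for that time. The documents do not support this, since the cross-reference to 14.0 probably makes 14.1 the governing text. It is a wording conflict worth removing, because the men's criterion 12 already states 90 days and 23.3 uses the same period for reporting pregnancies.

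**What to change.** Replace the counseling sentence in criterion 11 with wording such as: *Women of childbearing potential on MMF who are not abstinent must use an IUD as one of the two methods; oral and other systemic hormonal contraceptives count toward neither method.*

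Both halves are needed. A rule that asked only for one method MMF does not affect would presumably let spermicide fill that place and the pill remain as the second. Spermicide or another standard means can still serve as the second method beside the IUD.

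In the same edit, end criterion 11's contraception period 90 days after the final ixazomib dose, as 14.1 does, and use 14.1's definition of true abstinence.

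The cost is protocol wording only, with no added procedures or patients. The consent form should be checked and aligned if it differs. The downside is a narrower choice of contraception for at most 6 participants, possibly none.
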